# 1 SYNOPSIS

Title of Study:	A randomised, double-blind, placebo-controlled study to evaluate the micro-macroscopic effects on muscles, the safety and tolerability, and the efficacy of givinostat in patients with Becker Muscular Dystrophy
Protocol Number:	DSC/15/2357/53
Study Design:	This is a phase 2, randomised, double-blind, placebo-controlled study. Approximately 48 eligible patients will be randomized in a 2:1 ratio to be treated with givinostat or placebo for a period of 12 months.
Investigators/Study Sites:	The study will be conducted at 1-2 investigational site(s).
Phase of Development:	Phase 2
Objectives:	The primary objective is to establish the histological effects of givinostat versus placebo administered over 12 months.
	
 
The secondary objectives of this study are the following:
 
To establish the macroscopic muscle effects of givinostat versus placebo administered chronically over 12 months assessed by MRI/MRS.
 
To establish the other histological effects of givinostat versus placebo administered over 12 months.
 
To establish the efficacy of givinostat versus placebo administered chronically over 12 months in slowing disease progression.
 
To assess the safety and tolerability of givinostat versus placebo administered chronically.
 
To evaluate the pharmacokinetic (PK) profile of givinostat administered chronically in the target population.
 
To evaluate the impact of givinostat versus placebo administered chronically on quality of life and activities of daily living.
 
The exploratory objectives are the following: 
 
To evaluate the correlation between the PK profile of givinostat and pharmacodynamics (PD) data.
 
To evaluate a possible disease-related biomarker.
 
To explore additional disease-related MRI biomarkers.
 
 
 

Study Population:	The study will enroll adult male patients with an established molecular diagnosis of Becker Muscular Dystrophy (BMD).
Selection of	Patients must meet all of the following criteria in order to be included
Subjects:	in the study:
Subjects.	1. Ambulant male patients aged $\geq$ 18 years to $\leq$ 65 years at

17 June 2020 Page 4 of 110

- randomization with BMD diagnosis confirmed by genetic testing.
- Able and willing to give informed consent in writing.
- Able to perform 6MWT at screening with a minimum distance of 200 m and maximum distance of 450 m.
- 4. If in treatment with systemic corticosteroids and/or ACE inhibitor, and/or β or α adrenergic receptor blocker, no significant change in dosage or dosing regimen (excluding changes related to body weight change) for a minimum of 6 months immediately prior to start of study treatment.
- Patients must be willing to use adequate contraception.
   Contraceptive methods must be used from Randomization through 3 months after the last dose of study treatment.

Patients meeting any of the following criteria are ineligible to participate in this study:

- Exposure to another investigational drug within 3 months prior to the start of study treatment.
- Use of any pharmacologic treatment, other than corticosteroids, that might have an effect on muscle strength or function within 3 months prior to the start of study treatment (e.g., growth hormone). Vitamin D, calcium, and any other supplements will be allowed.
- Surgery that might affect muscle strength or function within 3 months before study entry or planned surgery at any time during the study.
- 4. Presence of other clinically significant disease that in the Investigator's opinion could adversely affect the safety of the patient, making it unlikely that the course of treatment or follow-up is completed, or could impair the assessment of study results.
- A diagnosis of other uncontrolled neurological diseases or presence of relevant somatic disorders not related to BMD that may interfere with the ability to perform the muscle function tests and/or to comply with the study protocol procedures.
- Platelet count, WBC count and hemoglobin at screening <
   Lower Limit of Normal (LLN). If laboratory screening results
   are < LLN, platelet count, WBC count and hemoglobin are to
   be repeated once, and if again < LLN become exclusionary.

- Symptomatic cardiomyopathy or heart failure (New York Heart Association Class III or IV) or left ventricular ejection fraction < 50% at screening or with heart transplant.

- Current liver disease or impairment, including but not limited to elevated total bilirubin (> 1.5 x ULN), unless secondary to Gilbert's disease or pattern consistent with Gilbert's disease.
- Inadequate renal function, as defined by serum Cystatin C > 2 x the upper limit of normal (ULN). If the value is > 2 x ULN,

17 June 2020 Page 5 of 110

	serum Cystatin C will be repeated once, and if again > 2 x ULN becomes exclusionary.  10. Positive test for hepatitis B surface antigen, hepatitis C antibody, or human immunodeficiency virus at screening.  11. Baseline corrected QT interval, Fridericia's correction (QTcF) > 450 msec, (as the mean of 3 consecutive readings 5 minutes apart) or history of additional risk factors for torsades de pointes (e.g., heart failure, hypokalemia, or family history of long QT syndrome).  12. Current psychiatric illness/social situations rendering the potential patient unable to understand and comply with the muscle function tests and/or with the study protocol procedures.  13. Hypersensitivity to the components of study medication.  14. Sorbitol intolerance or sorbitol malabsorption, or the hereditary form of fructose intolerance.  15. Contraindications to muscle biopsy.  16. Contraindications to MRI/MRS (e.g., claustrophobia, metal implants, or seizure disorder).  17. Hypertriglyceridemia (> 1.5 x upper limit of normal [ULN])*  * At screening, patients with hypertriglyceridemia can be enrolled if in stable treatment and with controlled levels of triglycerides (i.e. within normal range) for at least six months.		
Planned Sample	Approximately 48 patients are to be randomized.		
Size: Stratification:	The randomization process will be stratified by the concomitant		
	steroids use at baseline (yes vs. no).		
Randomization ratio:	The givinostat or placebo randomization ratio is 2:1.		
Study duration for participants:	The study is made up of a 4-week screening period, a 12-month treatment period and a 4-week follow-up period. The total study period for each patient is therefore of 14 months.		
Reference Therapy:	Givinostat or placebo oral suspension (10 mg/mL) twice daily (bid) (in a fed state) as described below:		
тистару.	(in a fed state) as described below.		
	Weight (kg) ≥30 and <50 ≥50 and <60 ≥60 and <70 ≥70		
	Dose (mg) bid 26.7 33.3 36.7 40 46.7		
	Oral suspension (mL) bid         2.7         3.3         3.7         4.0         4.7		
Criteria for Evaluation:	The primary efficacy assessment is Total fibrosis (%) assessed through histological examination of muscle biopsies.		

17 June 2020 Page 6 of 110

The secondary efficacy assessments are the following:

- Fat fraction of vastus lateralis and soleus evaluated by MRS technique
- Fat fraction of pelvic girdle and lower limb muscles evaluated by Dixon MRI technique
- CSA of pelvic girdle and lower limb muscles by means of Dixon MRI technique
- Other biopsy histological parameters (Cross-Sectional Area (CSA), Muscle Fiber Area Fraction [MFAF], regenerative fibers)
- Motor Function Measurement (MFM)
- Time Function Tests (TFT)
  - o Time to rise from floor
  - o Run/walk 10 m
  - Time to climb 4 standard steps
- Six Minute Walk Test (6MWT)
- Muscle strength evaluated by knee extension, elbow flexion as measured by Hand-Held Myometry (HHM)
- Quality of life (assessed by SF36)

Safety and tolerability will be evaluated by monitoring hematology and blood chemistry, coagulation, urinalysis, vital signs, physical examinations, weight, height, echocardiogram, ECG and respiratory function evaluation.

A blood sample will be collected during the study for LTBP4 and Osteopontin genotyping. Patients who have already concluded the study may be asked to return to the center for a blood sample collection

Blood sample collection for serum circulating proteins (by an ELISA based system) at randomization, 6 months and at the end of treatment.

Blood samples will be obtained for PK analysis of givinostat and its metabolites.

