### 6 INVESTIGATIONAL PLAN

# 6.1 Description of Overall Study Design and Plan

This is a Phase 2, randomised, double-blind, placebo-controlled study. Ambulant patients who have provided written informed consent will undergo a 4-week screening period to determine eligibility for the study. Approximately 48 eligible patients will then be randomized in a 2:1 ratio to be treated with givinostat or placebo for a period of 12 months. The randomization process will be stratified by the factor related to concomitant steroid use at baseline (yes vs. no). Patients who complete the study (i.e. 12 months of treatment) will be asked to return for a follow-up visit 4 weeks after the end of treatment.

An overview of the study is provided in Figure 1.

Figure 1: Study Design

A total of 12 visits will take place during the study: Screening (V1, V2), Randomization (V3), Treatment (V4-V10), End of Study (V11) and Follow-up (V12). Visits during the treatment period will take place every 12 weeks except for the first 2 months, when they will occur every 2 weeks to allow close monitoring of hematological safety parameters. Patients may be evaluated more often if necessary, for safety reasons. Patients who discontinue the study treatment early will be asked to come in for an Early Withdrawal Visit within 4 weeks

17 June 2020 Page 43 of 110

after the last dose of study treatment. Patients who have ongoing AEs at discontinuation will be followed until resolution or stabilization.

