# 6.2 Discussion of Study Design

This study has been designed as a conventional parallel-group design. Since the study will be conducted in a population with a serious and life-threatening disease, the unequal randomization ratio (2:1 givinostat vs. placebo) will be applied to reduce the exposure to placebo. A 2:1 randomization also provides for an increased number of patients who are exposed to givinostat. The randomization process will be stratified by the factor related to concomitant steroid use at baseline (yes vs. no).

Considering a 5% of unevaluable baseline biopsies, 51 patients will be randomized in the study to have 48 fully evaluable patients.

After the first 20 baseline muscle biopsies were collected, a blinded interim analysis was planned, aimed at checking the variability of the original primary endpoint (i.e. CSA). The observed variability of the original primary endpoint was very large, leading to a revision of the primary endpoint to % total fibrosis. The sample size was amended accordingly to require a total of 51 patient to be randomized on a 2:1 basis.

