# 13.1 Determination of Sample Size

The hypothesis to be tested in this study is as follows:

$$H_0: \mu_G - \mu_P = 0$$
 vs  $H_1: \mu_G - \mu_P \neq 0$ 

where  $\mu_G$  and  $\mu_P$  the mean change from baseline to 12 months in total fibrosis (%) for the givinostat and placebo groups respectively.

A sample size of 48 patients with evaluable baseline biopsies (in a 2:1 ratio, 32 and 16 respectively) will provide 80% power to test the null hypothesis of no treatment effect (givinostat – placebo) on total fibrosis vs the alternative hypothesis that the treatment effect is  $\geq$  9% using a two-sided t-test with alpha level of 5% and assuming a common SD of 10% (with the SD being based upon blinded interim data from first 20 patients with valid pre and post-treatment biopsies).

Allowing for an approximate 5% of patients with unevaluable biopsies, the total number of patients to be randomized is 51 (i.e. 34 in givinostat arm and 17 in placebo arm).

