3. BACKGROUND AND RATIONALE

3.1. Overall Study Design and Plan Description

This is a phase 2, randomized, double-blind, placebo-controlled study. Ambulant patients who have provided written informed consent will undergo a 4-week screening period to determine eligibility for the study. Approximately 51 eligible patients will then be randomized in a 2:1 ratio to be treated with givinostat or placebo for a period of 12 months. The randomization process will be stratified by the factor related to the concomitant steroids use at baseline (yes vs. no). Patients who complete the study (i.e. 12 months of treatment) will be asked to return for a follow-up visit 4 weeks after the end of treatment.

An overview of the study is provided in Figur.

Figure 1: Study Design

Sponsor: ITALFARMACO
Protocol: DSC/15/2357/53

A total of 12 visits will take place during the study: Screening (V1, V2), Randomization (V3), Treatment (V4-V10), End of Study (V11) and Follow-up (V12). Visits during the treatment period will take place every 12 weeks except for the first 2 months, when they will occur every 2 weeks to allow close monitoring of hematological safety parameters. Patients may be evaluated more often if necessary, for safety reasons. Patients who discontinue the study treatment early will be asked to come in for an Early Withdrawal Visit within 4 weeks after the last dose of study treatment. Patients who have ongoing AEs at discontinuation will be followed until resolution or stabilization.

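### The protocol gives two numbers to randomise, about 48 and 51; in three places the evaluable target of 48 stands where the randomised number should be

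*Protocol*

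**What the plan says.** Three places in the current protocol give about 48 as the number to randomise:

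- Synopsis, Study Design: "Approximately 48 eligible patients will be randomized in a 2:1 ratio to be treated with givinostat or placebo".
- Synopsis, Planned Sample Size: "Approximately 48 patients are to be randomized".
- Section 6.1: "Approximately 48 eligible patients will then be randomized in a 2:1 ratio".

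Six places in the current documents give 51:

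- Protocol section 13.1: "the total number of patients to be randomized is 51 (i.e. 34 in givinostat arm and 17 in placebo arm". The synopsis's sample size paragraph and SAP section 3.5 say the same, with the same split.
- Protocol section 6.2: "51 patients will be randomized in the study to have 48 fully evaluable patients". It adds that the sample size was amended to 51.
- SAP section 3.1: "Approximately 51 eligible patients will then be randomized in a 2:1 ratio". SAP section 3.3.2 agrees.

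The calculation behind these figures is in protocol section 13.1. It asks for 48 evaluable patients (32 and 16) for 80% power, to detect a 9-point difference with an SD of 10, using a two-sided t-test at 5%. It then allows for about 5% unevaluable biopsies. Section 7 says that patients who drop out before the end of treatment are not replaced.

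**The concern.** The number to be randomised is a basic design figure, and one protocol version gives two answers. The synopsis disagrees with itself, and so do the adjacent sections 6.1 and 6.2. None of this is amendment history; all of it is operative text.

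A reader who takes the Planned Sample Size entry at face value would treat 48 randomised patients as full recruitment. The 5% allowance in section 13.1 would then have been dropped, and the evaluable target could be met only if no biopsy were lost. Lost biopsies would not be recovered in the main analysis: dropouts are not replaced, and SAP section 6.3.1 bases the primary analysis on observed data only. At the reporting stage, the question whether the trial reached its planned size would have two answers.

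**Working it through.** **Inputs.** Difference 9, SD 10, two-sided alpha 0.05, allocation 2:1, 48 evaluable (32 and 16), 5% unevaluable, 51 randomised (34 and 17). All are from protocol section 13.1.

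**Step 1: reproduce the 48.** Exact two-sample t-test. The noncentrality is 9 / (10 × √(1/n₁ + 1/n₂)) on n₁ + n₂ − 2 degrees of freedom.

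- 32 and 16: noncentrality 2.94 on 46 df, power 82.1%.
- 30 and 15: noncentrality 2.85 on 43 df, power 79.4%.

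So 48 is the smallest whole 2:1 design with at least 80% power. The excess over 80% comes from rounding up to a multiple of three.

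**Step 2: reproduce the 51.** 48 / 0.95 = 50.5, rounded up to 51, which splits exactly into 34 and 17. The stated figure is right.

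**Step 3: apply the plan's own 5% loss to each candidate number.**

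| Randomised | Evaluable after 5% loss | Against the target of 48 | Power |
|---|---|---|---|
| 51 | 51 × 0.95 = 48.5 (32.3 and 16.15) | met | 82.4% |
| 48 | 48 × 0.95 = 45.6 (30.4 and 15.2) | short by 2.4 | 80.0% |

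In whole patients, the second row depends on which arm loses biopsies:

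- 30 and 15: 79.4%
- 31 and 15: 79.9%
- 30 and 16: 81.1%

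**Step 4: can the two numbers be the same number, loosely stated?** They differ by 51 − 48 = 3 patients, or 3/51 = 5.9%. That gap is the allowance itself. Section 6.2 names both numbers in one sentence and gives each its own role. SAP section 3.1 has nearly the same sentence as protocol section 6.1, with 51 where the protocol has 48.

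**The case against.** The strongest reply is that the intended number is not in doubt. The synopsis's sample size paragraph gives 51 with its derivation and its split by arm, and section 6.2, directly after 6.1, repeats it. The three entries with 48 are summary lines that say *approximately*, and the power at stake is small. Most of this stands. The intended number can be recovered, and the calculation in section 13.1 is correct. *Approximately* does not close the gap, however, because 48 already has a defined meaning as the evaluable count.

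Four stronger readings are tempting, and the documents do not support them.

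- *The trial is underpowered.* The stated power is 80%. With 48 randomised and a 5% loss it is about 79% to 81%, so the stated power is essentially kept.
- *Power would fall to about 73%.* That needs losses the plan does not state. For example, assume 5% lost at each of two biopsies and 10% dropout: 48 × 0.95 × 0.95 × 0.90 = 39 pairs, and 26 and 13 give 73.2%. On the same assumptions 51 randomised leaves 41.4 pairs, and 27 and 14 give 76.0%. Most of the fall comes from the assumed losses; the choice between 48 and 51 accounts for less than 3 points.
- *Recruitment could still be stopped at 48.* SAP sections 3.5 and 6.6, in the version of 25 June 2020, describe enrolment as completed. Protocol section 13.10, dated 17 June 2020, still places that in the future, so the closing date is not known, but the risk has probably passed.
- *The synopsis figure is the official target.* Nothing in either document ranks the Planned Sample Size entry above section 13.1.

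**Conclusion.** The inconsistency is real and is in current text: three entries give about 48 to randomise and six give 51. The likely explanation is that the three were not updated when the sample size was amended. The consequence is limited. Randomising 48 would miss the evaluable target by 2 to 3 patients and cost about 2.4 points of power (82.4% against 80.0%) at the plan's own loss rate.

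These power figures rest on the section 13.1 assumptions: a t-test on the original scale, a difference of 9, an SD of 10, and 5% loss spread evenly over the arms except where whole-patient splits are shown. They do not describe the log-scale ANCOVA that the SAP makes primary. The point itself does not depend on them, because the two numbers conflict whatever the power. What remains at stake is a single, clear planned number for the final report.

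**What to change.** In the synopsis (Study Design and Planned Sample Size) and in section 6.1, replace 48 by 51, with 34 on givinostat and 17 on placebo. Keep 48 only where it denotes evaluable patients, as sections 6.2 and 13.1 already do. The SAP needs no change on this point.

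The cost is a wording correction in three places, with no recalculation and no effect on the analysis. If the protocol will not be amended again, the clinical study report can state that the planned number randomised was 51 and that the three entries with 48 refer to the evaluable target.

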### Study Endpoints:

Primary endpoint: Mean change in total fibrosis (%) comparing the histology of muscle biopsies before and after 12 months of treatment with givinostat versus placebo.

### Secondary endpoints:

- Mean change in fat fraction of vastus lateralis and soleus comparing Magnetic Resonance Spectroscopy (MRS) before and after 12 months of treatment with givinostat versus placebo.
- Mean change in fat fraction of pelvic girdle and lower limb muscles comparing Magnetic Resonance Imaging (MRI) before and after 12 months of treatment with givinostat versus

17 June 2020 Page 7 of 110

placebo.

- Mean CSA of pelvic girdle and lower limb muscles comparing MRI before and after 12 months of treatment with givinostat versus placebo.
- Mean change in other histology parameters (e.g. Cross-Sectional Area (CSA), MFAF, regenerative fibers) comparing the histology biopsies before and after 12 months of treatment with givinostat.
- Mean change in Motor Function Measurement (MFM) before and after 12 months of treatment with givinostat versus placebo.
- Mean change in Time Function Tests (time to climb four standard steps, time to rise from floor and time to walk/run 10 m) before and after 12 months of treatment with givinostat versus placebo
- Mean change in 6 Minute Walking Test (6MWT) before and after 12 months of treatment with givinostat versus placebo.
- Proportion of patients with < 10% worsening in 6MWT at the end of study.
- Proportion of patients who lose the ability to rise from floor (Baseline through end of study).
- Proportion of patients who lose ambulation during the study.
- Mean change in muscle strength evaluated by knee extension, elbow flexion as measured by Hand Held Myometry (HHM), before and after 12 months of treatment with givinostat versus placebo.
- Mean changes in quality of life (assessed by the 36-item Short Form survey [SF36]) before and after 12 months of treatment with givinostat as compared to placebo.

### Safety endpoints:

- Number of patients experiencing treatment-emergent adverse events (TEAEs) and serious adverse events (SAEs) from Baseline through end of study (EOS).
- Type, incidence, and severity of TEAEs and SAEs (Baseline through EOS).
- Changes from baseline to end of study of:
  - Vital signs and clinical laboratory tests (blood chemistry and hematology).
  - Physical examination.
  - Pulmonary function evaluated by Forced Vital Capacity (FVC), Forced Expiratory Volume at 1 second (FEV1), FVC/FEV1, Peak Expiratory Flow (PEF).
  - Cardiac function evaluated by ECG and ECHO.
  - Weight, height, and body mass index (BMI).

17 June 2020 Page 8 of 110

	Pharmacokinetic endpoints
	
 
Description of the PK of givinostat and its major metabolites: ITF2374 and ITF2375.
 

	
 
Exploratory endpoints:
 
PK-PD analyses of the relationship between metrics of exposure and the efficacy/safety endpoints of givinostat.
 
Analyses to explore whether the effects of givinostat versus placebo administered chronically may be related to the type of LTBP4 or osteopontin genotype.
 
Evaluation of serum circulating proteins, by an ELISA based system, as potential biomarkers for BMD.
 
Additional evaluations of other muscle image parameters assessed by MRI (details will be provided in a specific imaging protocol).
 

Rules for cessation of randomised treatment in an individual participant:	The Study treatment should be permanently discontinued if any of the following events occur:  • Severe drug-related diarrhea (increase of ≥ 7 stools per day)  • Any drug-related SAE  • QTcF > 500 msec  • Platelet count ≤ 50 x 10  /L (see protocol for details)
	
 
White blood cell count ≤ 2.0 x 10^9/L (see protocol for details)
 
Hemoglobin ≤ 8.0 g/dL (see protocol for details)
 

Rules for temporary interruption of randomised treatment in an individual participant and dose modification	The Study treatment should be temporarily interrupted if any of the following events occur, see protocol for details:  • Moderate or severe diarrhea (increase more than 4 stools/day).  • Platelet count < 75 x 10  /L but > 50 x 10  /L.  • White blood cell < 3.0 x 10  /L but > 2.0 x 10  /L.  • Hemoglobin < 10.0 g/dL but > 8.0 g/dL  • Triglycerides >300 mg/dL*
	Study treatment can be resumed at a level 20% smaller than the dose at which an AE leading to a temporary stop occurred, once platelets and/or white blood cell and/or hemoglobin and/or triglycerides are normalized or when diarrhea is mild.
	*Treatment for high triglycerides can be prescribed by the investigator if values are above ULN.
Sample size calculation:	The primary hypothesis to be tested in this study is that total fibrosis (%) will increase less in the givinostat group than in the placebo group. The primary endpoint of the study is the mean change from baseline to 12 months in total fibrosis (assuming normal distribution).

17 June 2020 Page 9 of 110

A sample size of 48 patients with evaluable baseline biopsies (in a 2:1 ratio, 32 and 16 respectively) will provide 80% power to test the null hypothesis of no treatment effect (givinostat – placebo) on total fibrosis vs the alternative hypothesis that the treatment effect is  $\geq$  9% using a two-sided t-test with alpha level of 5% and assuming a common SD of 10% (with the SD being based upon blinded interim data from first 20 patients with valid biopsies).

Allowing for an approximate 5% of patients with not evaluable biopsies, the total number of patients to be randomized is 51 (i.e. 34 in givinostat arm and 17 in placebo arm).

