## 9.1.10 Visit 11: End of Study Visit (EOS, Week 48 ± 7 days) and early withdrawal visit

The EOS (Visit 11) will be scheduled at the end of treatment (i.e., 48 weeks after the Randomization Visit,  $\pm$  7 days). Patients will be instructed to take the morning dose at the site in case of pre-dose PK analysis.

Patients who prematurely withdraw from the study for any reason will undergo an Early Withdrawal Visit within four weeks after the last dose of study treatment. The Early Withdrawal Visit requirements are the same as those of the EOS Visit described in this section.

The following assessments will be performed during this visit:

- Concomitant medications
- Physical examination
- Vital signs (blood pressure, heart rate and body temperature)
- Weight
- Height
- 12-lead ECG
- Echocardiogram
- Pulmonary function tests: FEV1, FVC, FEV1/FVC, and PEF
- Blood collection for
  - hematology
  - blood chemistry
  - coagulation tests (PT and aPTT)
  - thyroid function tests (TSH, fT3, fT4)
  - PK analysis
  - Biomarker analysis
- Urine analysis;
- 6MWT + MFM
- Muscle strength test (knee extension and elbow flexion by HHM)
- Timed function tests
- Quality of Life test (assessed by SF-36)
- AE assessments

17 June 2020 Page 68 of 110

- Diary return and patient compliance
- MRI/MRS and muscle biopsy evaluations, which may be performed on different days (in case of early withdrawal visit the MRI/MRS and Quality of Life test do not have to be performed). Treatment is to continue up to the last assessment.

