6.3.4. Measurement of Treatment Compliance

For each patient, the compliance will be calculated according to the following formula:

$$Compliance_{ji} = \frac{((number\ of\ days\ from\ last\ evaluation_{ji}*\ 2) - number\ of\ doses\ not\ taken_{ji})}{number\ of\ days\ from\ the\ last\ visit\ _{ji}*\ 2}$$

where j = patient 1, 2... and <math>i = visit 8, 9, 10 and 11.

The total compliance for each patient will be computed as the sum of the compliance at visit 8, 9, 10 and 11.

Total compliance will be summarized as <80% and 80-100%. The compliance will be also summarized as a continuous variable using descriptive statistics.

Treatment compliance will be calculated on ITT set using the information about doses not taken reported in the study diary or in the eCRF if no diary available.

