6.4.1. Extent of Exposure

The exposure to the study treatment will be evaluated by means of the variables defined below.

The following definitions will be applied in the variable calculation:

- First drug administration: it is the earliest date when a non-zero dose of study treatment was administered and recorded on the eCRF.
- Last drug administration: it is the latest date when a non-zero dose of study treatment was administered and recorded on the eCRF.

The duration of exposure to study treatment is calculated as:

Duration of exposure (days) = (Date of Last drug administration - Date of First drug administration + 1).

The duration of exposure to study treatment includes the periods of temporary interruption of the study treatment for any reason.

The duration of actual exposure to study treatment will be calculated excluding the periods of temporary interruption of the study treatment for any reason.

Ver.04 25Jun2020

Sponsor: ITALFARMACO Protocol: DSC/15/2357/53

The total daily dose in mg (i.e. mL X 10 = mg) will be calculated as the total amount of drug administered during the study divided by the duration of actual exposure.

The duration of exposure to study treatment, the duration of actual exposure to study treatment and the total daily dose will be summarized by means of the usual descriptive statistics on the Safety Analysis Set overall and by treatment group.

The number and percentage of subjects with and without any IMP modification, as well as the number and percentage of subjects with each type of IMP modification (dose increased, dose reduced, dose permanently stopped, dose temporarily stopped) and the reason for the modification (Adverse event/Lab or ECG abnormality, dosing error, other) will be summarized by treatment group.

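### The SAP compliance formula counts every calendar day as a dosing day, including days on which the protocol withholds drug, so compliance can be under- or over-scored

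*Protocol*

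**What the plan says.** SAP 6.3.4 computes compliance at Visits 8, 9, 10 and 11. Doses due are the days since the previous evaluation or visit, times two. The numerator is that figure minus the doses not taken, and the source is described as "using the information about doses not taken reported in the study diary or in the eCRF if no diary available". The section then says "The total compliance for each patient will be computed as the sum of the compliance at visit 8, 9, 10 and 11", with classes given by "Total compliance will be summarized as <80% and 80-100"%.

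The protocol requires days off drug. For listed diarrhea, platelet, white cell, hemoglobin and triglyceride events, the Synopsis states "The Study treatment should be temporarily interrupted if any of the following events occur, see protocol for details". Section 7.3.1 repeats this, has the blood counts retested until normal, and adds permanent stops and stops pending a repeat test. Under Protocol 9.1.10, a patient who withdraws early "will undergo an Early Withdrawal Visit within four weeks after the last dose of study treatment". Table 5 makes that visit the same as Visit 11, and diary return is part of it, so it closes a compliance interval.

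SAP 6.4.1 does separate these days for exposure: "The duration of actual exposure to study treatment will be calculated excluding the periods of temporary interruption of the study treatment for any reason". SAP 6.3.4 has no matching exclusion. Protocol 8.6 says only that the diary shows how many doses the patient actually took.

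**The concern.** A compliance ratio should compare doses taken with doses the patient was meant to take. In SAP 6.3.4 the denominator includes days on which the protocol tells him not to dose. The plan also leaves open whether a withheld dose is a dose not taken, so two programmers could derive different figures from the same data. Neither choice repairs the denominator.

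The interruption and stopping rules cover platelet falls and diarrhea, which Protocol 4.2.2 describes as the most frequent adverse events on givinostat. The error is therefore likely to fall more on that arm, and a reported difference in compliance between arms would partly reflect toxicity.

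**Working it through.** The plan states no compliance figure to reproduce, so the check applies the formula to defined patients.

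Inputs:
- Two doses a day (Protocol 8.2.2).
- 84 days between compliance visits, four intervals, 336 days in all (Protocol 6.1, Table 5).
- Hold of 14 to 21 days. This is an assumption: Protocol 4.2.2 reports platelet recovery within 2 to 3 weeks of discontinuation in earlier studies.
- Gap of up to 28 days from last dose to early withdrawal visit (Protocol 9.1.10).
- The same day count in numerator and denominator, starting at first dose for the first interval. This is also an assumption, because SAP 6.3.4 words the two counts differently.

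Let D be the days in the interval, I the days off drug by rule, and m the other missed doses.
- Withheld doses recorded as not taken: (2D − 2I − m) / 2D
- Withheld doses not recorded: (2D − m) / 2D
- Prescribed days only: (2(D − I) − m) / (2(D − I))

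**Hold, nothing else missed (m = 0), withheld doses recorded**
- I = 14, D = 84: (168 − 28)/168 = 83.3%
- I = 21, D = 84: (168 − 42)/168 = 75.0%
- I = 14, D = 336: (672 − 28)/672 = 95.8%
- I = 21, D = 336: (672 − 42)/672 = 93.8%

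On prescribed days each of these is 100%. If withheld doses are not recorded, the formula also gives 100%. Over 336 days, a fully adherent patient falls below 80% only after more than 0.2 × 336 = 67.2 days off.

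**Hold of 21 days with 6 other missed doses, D = 84**
- Recorded: (168 − 42 − 6)/168 = 71.4%
- Not recorded: (168 − 6)/168 = 96.4%
- Prescribed days only: (126 − 6)/126 = 95.2%

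**Permanent stop on day 28, so 56 doses due, with the visit g days after the last dose**

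| g (days) | All 56 taken; withheld doses recorded | 14 of 56 missed; withheld doses not recorded |
|---|---|---|
| 7 | 56/70 = 80.0% | (70 − 14)/70 = 80.0% |
| 14 | 56/84 = 66.7% | (84 − 14)/84 = 83.3% |
| 28 | 56/112 = 50.0% | (112 − 14)/112 = 87.5% |
| Prescribed days only | 56/56 = 100% | 42/56 = 75.0% |

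This patient has only one compliance interval, so his total does not depend on how intervals are combined. With a 28-day gap, a fully adherent patient is placed below 80%, and a patient at 75% is placed in the 80-100% class.

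**The case against.** The strongest reply is that withheld doses may never be entered as not taken. SAP 6.4.1 summarizes temporary and permanent stops separately as treatment modifications with reasons, so the diary item may mean only doses the patient forgot. A fully adherent patient then scores 100%, which is right. This stands, and it defeats any claim that every patient who obeys the safety rules gets a wrong figure. It does not rescue the denominator, because patients who also missed doses are over-scored, noticeably so after an early stop.

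A second reply is that a reader can separate adherence from toxicity with the exposure and modification tables in SAP 6.4.1 and Protocol 13.4. That limits the harm but does not correct the compliance table.

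Three stronger readings are tempting and not supported:
- That a single 2 to 3 week hold puts a patient in the lower class. The classes apply to total compliance, and the 48-week figure stays at 94% to 96%.
- That a late stop does so. For a stop 10 days after Visit 9 with the visit 28 days later, the last interval is 20/76 = 26.3%. An unweighted mean with two full intervals is 75%, but pooling days gives (84 + 84 + 10)/206 = 178/206 = 86.4%. The SAP specifies neither the mean nor pooling; it specifies a sum, which is a separate problem.
- That patients with toxicity would leave the per-protocol set. The exclusion rules are in a separate document (Protocol 13.2.2, SAP 5), and nothing here links them to compliance.

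Nor can the 3 of 21 interruptions in Protocol Amendment No. 2 be carried forward as a rate. They arose under the earlier, higher starting dose.

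**Conclusion.** The concern holds as a wrong denominator in SAP 6.3.4, and no other section corrects it. The direction of error depends on how withheld doses are recorded, which the documents do not settle. The error is modest for one hold viewed over 48 weeks (4 to 6 points for a fully adherent patient if withheld doses are recorded). It is large for early permanent stops: 50 points too low, or 12.5 points too high, in the day-28 example with the maximum four-week gap. A shorter gap shrinks both.

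The affected output is descriptive; no efficacy model or analysis set in these documents uses it. That the error falls more on the givinostat arm is an expectation from the known platelet effect, not something that these documents measure.

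**What to change.** Change SAP 6.3.4 only; no clinical rule changes.

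- Count doses due on prescribed dosing days only: from the previous diary check (or first dose) to the earlier of the visit and the last prescribed dose, minus interruptions ordered by the protocol or the investigator.
- Use those same days in numerator and denominator.
- State that withheld doses are not counted as not taken.

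The interruption dates are already needed for SAP 6.4.1, but that section removes gaps for any reason. Reusing it unchanged would also remove gaps the patient chose himself and inflate compliance. Ordered interruptions should be selected by the recorded reason for the treatment modification. SAP 6.4.1 lists an other category among the reasons, so those entries need a classification rule set before unblinding.

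The cost is a sentence or two in the SAP and a small amount of programming, including the reason filter. The downside is that compliance would no longer reflect dose intensity, which SAP 6.4.1 already reports through actual exposure and daily dose.
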